4.4.2 Analysis of Secondary Efficacy Parameters

Patency of the HAV (primary, primary assisted, secondary) rates will be presented for Months 3, 6 and 9.

Clopper-Pearson CIs will be presented for frequency counts of patency rates.

The HAV interventions and type of interventions needed to maintain / restore patency in the HAV through Month 12 will be descriptively summarized. Interventions will be recorded at each study visit and interventions occurring after the Month 12 visit will be provided in a listing.

Number of patients, who needed any intervention to maintain / restore patency throughout the study will be tabulated by counts and frequencies. The cumulative number of patients with any intervention needed will be presented stratified by visit and the number of patients having 1, 2, 3, etc. interventions will be presented.

Due to the nature of the study, an intervention can occur between planned study visits and will be recorded in the EDC as an unscheduled visit. A "by visit" summary will represent the intervention information that occurred before and on the scheduled visit. For example, the summary at Day 5 will denote the information from all interventions that occurred up to Day 5 visit and on the Day 5 visit. Similarly, the Day 29 summary will denote the information from all interventions that occurred after Day 5, and up to Day 29 (inclusive of Day 29).

VascuQol PAD symptom assessment data

The VascuQol PAD symptom assessment consists of 25 questions. The total score and the 5 domain scores (Activity, Symptom, Pain, Emotional, and Social) will be recorded in the clinical database. Total score and each domain score will be presented by descriptive measures for each visit as well as for the absolute change from baseline. Individual data, domain score and total score will also be listed.

The 1-year analysis will provide the table summary by planned visit up to Month 12. The final analysis will only display results in a listing.

ABI and 6 minute walk test

ABI and 6 minute walk test will be presented by descriptive measures for each visit as well as for the absolute change from baseline. Data will also be listed.

Statistical Analysis Plan	Final Analysis
CLN-PRO-004	16/23

The 1-year analysis will provide the table summary by planned visit up to Month 12. The final analysis will only display results in a listing.

HAV Remodeling by CT angiography and US at Months 1 (Day 29), 6, 12, and 60 will be presented descriptively. Data will also be listed.

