## 2.4.3. CLN-PRO-V002 Study Results (24 M)

Recruitment began in October 2013 and was completed in June 2014 with 20 patients implanted. Thirteen patients completed the 2 year follow up visit. Of the seven patients terminating the study early, three died and four were withdrawn after occlusion of the HAV. None of the deaths were considered related to the investigational device or procedure.

Kaplan-Meier analyses in which deaths were censored revealed primary, primary assisted, and secondary patency probability rates of 79.2%, 79.0%, and 89.5% at Week 26, 63.3%, 63.2%, and 84.2% at Month 12, 63.3%, 63.2%, and 79.0% at Month 18, and 58.1%, 57.9%, and 73.7% at Month 24.

Six patients (30%) required at least 1 graft intervention to maintain or restore HAV patency during the study. Four patients required 1 intervention and 1 patient each required 3 and 4 interventions. Most interventions successfully restored patency. However, in 1 patient the graft patency could not be restored and the HAV was replaced with an alternative bypass graft. Two patients, who had previously undergone successful interventions, developed a recurrent thrombosis which was not treated and the HAV was left occluded. Two patients experienced HAV thrombosis with no or minimal symptoms and refused interventions on the HAV.

Confidential

All 20 patients experienced AEs (a total of 92 events). Thirty-one of these events in 13 patients were considered serious. The most frequent AEs reported included graft thrombosis (35% of patients), anastomotic stenosis (20% of patients), lymphocele (20% of patients), and local swelling (15% of patient). Those serious adverse events (SAEs) reported by at least 2 patients were graft thrombosis (6 patients, 30%) and anastomotic stenosis (2 patients, 10%).

No patient showed an increase in PRA levels. Two patients had a significant (>2-fold) increase from baseline in IgG levels. One of these patients experienced a thrombosis of the HAV between 3 and 6 months after implantation, while the other patient has had no HAV-related AEs and continues to have primary patency. Neither patient has had any evidence of dilatation or structural degeneration of the HAV.

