#### Efficacy:

- To determine the patency of the HAV (primary, primary assisted and secondary) at Months 3, 6 and 9
- To determine the rates of interventions needed to maintain / restore patency in the HAV through Month 12
- To assess effect of HAV implantation on symptoms of PAD using the VascuQol instrument
- To assess effect of the HAV on ABI
- To assess effect of the HAV on 6 minute walk test

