1.4 Objectives

1.4.1 Primary Objectives:

This is an open label Phase 2 study. There is no formal hypothesis testing.

Statistical Analysis Plan	
CLN-PRO-004	

Final Analysis 8/23

Safety:

• To evaluate the safety and tolerability of the Humacyte HAV in PAD patients undergoing femoro-popliteal bypass surgery

Efficacy:

- To determine the patency (primary, primary assisted and secondary) rate of the Humacyte HAV at Month 12
- To determine the incidence of hemodynamically significant stenosis (>70%) defined by duplex ultrasound, and the time to stenosis development

1.4.2 Secondary Objectives:

Safety:

- To assess changes in the panel reactive antibodies (PRA) response after HAV implantation
- To determine mechanical stability of the HAV based on freedom from aneurysmal degeneration on duplex ultrasound and computed tomography (CT) imaging
- To determine HAV durability in terms of freedom from need for HAV explanation or replacement due to infection, bleeding or conduit degeneration

Efficacy:

- To determine the patency of the HAV (primary, primary assisted and secondary) at Months 3, 6 and 9
- To determine the rates of interventions needed to maintain / restore patency in the HAV through Month 12
- To assess effect of HAV implantation on symptoms of PAD using the VascuQol instrument
- To assess effect of the HAV on ankle-brachial index (ABI)
- To assess effect of the HAV on 6 minute walk test

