1.5 Sample Size Estimation

Up to 25 patients were planned, and 15 patients were recruited into the study. As this Phase 2 study is one of the first studies of the HAV in humans with PAD, the number of patients was chosen in order to provide preliminary evidence of safety and efficacy of the HAV to allow the initiation of further trials in larger numbers of patients.

The study is not powered to assess the efficacy of the HAV.

2 Efficacy and Safety Variables

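### SAP 4.4.2 summarises ABI, 6 minute walk and VascuQol without regard to HAV status, exit after HAV loss, or replacement of the HAV

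*SAP*

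**What the plan says.** Protocol 3.2 lists among its secondary efficacy objectives "To assess effect of the HAV on ABI", with parallel objectives for the 6 minute walk test and for PAD symptoms on VascuQol. SAP 1.4 repeats them.

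The analysis is in SAP 4.4.2. For the first two measures, "ABI and 6 minute walk test will be presented by descriptive measures for each visit as well as for the absolute change from baseline". For VascuQol, "Total score and each domain score will be presented by descriptive measures for each visit as well as for the absolute change from baseline". The statistics are those of SAP 4: n, mean, SD, median, range and quartiles. SAP 3.3 bases every analysis on the single set of HAV recipients.

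Nothing in these sections says what to do with a value taken after the HAV has occluded, been abandoned or been replaced. SAP 7.2 deals with missing values only by imputing partial dates. The rule that treats early discontinuation as failure (Protocol 9.3), and the Kaplan-Meier version that does the same (SAP 4.4.1), apply to patency alone.

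Two provisions govern exit. Protocol 7.5.5 asks a patient who withdraws before Month 12 to have the Month 12 assessments at an ET visit. SAP 1.3 gives that combined visit the table label Month 12.

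**The concern.** There is no control arm, so change from baseline is the main evidence on these three objectives. The planned summary uses whatever values exist at a visit. Three things then happen without being stated:

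- **Exit after HAV loss.** The patient is absent from later rows: ABI and VascuQol at Months 3, 6 and 9, the walk test at Month 3, and all three at Month 12 if the patient dies, is lost or misses the ET visit. If those patients did worse, the remaining mean is too favourable.
- **ET attendance.** The value is kept, but one taken well before a year is shown as a Month 12 result.
- **Replacement or other revascularisation of the limb.** Later values partly reflect the other procedure but are summarised under the effect of the HAV.

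Protocol 2.5.3 intends a comparison with historical data on synthetic grafts, and Protocol 9.3 says the results will be used to size later studies. A functional gain with an unclear denominator would carry into both uses.

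**Working it through.** **Is there a figure in the plan to reproduce?** No. SAP 1.5 states "The study is not powered to assess the efficacy of the HAV", and neither document gives an expected change or SD for these measures. The sizes below are therefore illustrations on stated assumptions.

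**Inputs from the documents**
- Number of patients: "Up to 25 patients were planned, and 15 patients were recruited into the study" (SAP 1.5). All 15 are taken here as implanted.
- Earlier PAD study CLN-PRO-V002 (Protocol 2.4.3): 20 implanted and seven early exits, of which three were deaths and "four were withdrawn after occlusion of the HAV". Check: 3 + 4 = 7 and 20 - 7 = 13 completers, as stated.
- In one V002 patient "the HAV was replaced with an alternative bypass graft".
- V002 secondary patency at Month 12: 84.2%, which equals 16/19. Loss = 100 - 84.2 = 15.8%.

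**Assumptions**
- ABI gain g = 0.3 to 0.4 with a patent HAV.
- Change c = 0 after loss.
- Fraction lost p = 15.8% (V002) or 25% (a less favourable case).
- No patient with HAV loss supplies a value. This makes it an upper case.

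**Exit after HAV loss**
- Attenders-only mean = g. All-patient mean = (1 - p)g + pc. Overstatement = p(g - c), which is pg when c = 0.
- p = 0.158: 0.158 x 0.3 = 0.047 and 0.158 x 0.4 = 0.063. Relative to the all-patient mean: 0.158/0.842 = 19%.
- p = 0.25: 0.25 x 0.3 = 0.075 and 0.25 x 0.4 = 0.100. Relative: 0.25/0.75 = 33%.
- In patients: 15 x 0.158 = 2.4 and 15 x 0.25 = 3.75, so two to four people.
- Worked case: 3 of 15 lost, g = 0.30, c = 0. All-patient mean = 12 x 0.30/15 = 0.24, against 0.30 among attenders, a difference of 0.06.
- Wider range: with g = 0.2 to 0.4, c = 0 to -0.1 and 2 to 5 of 15 lost, the overstatement runs from 2 x 0.2/15 = 0.03 to 5 x 0.5/15 = 0.17.

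**Replacement**
- If the new graft gives gain g where an occluded HAV would give c, each such patient raises the 15-patient mean by (g - c)/15. That is 0.2/15 = 0.013 to 0.5/15 = 0.033 over the same wider range.

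**How likely are the events?**
- At V002's rates, the chance of at least one withdrawal after occlusion among 15 is 1 - 0.80^15 = 96%, and of at least one replacement 1 - 0.95^15 = 54%.
- These rates cover 24 months, so the chances by Month 12 may be lower. They are also imprecise: the exact 95% intervals are 5.7% to 43.7% for 4/20 and 0.1% to 24.9% for 1/20.

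**The case against.** The best reply is that failures are not simply lost at Month 12. Protocol 7.5.5 asks early leavers to have every Month 12 assessment, and the ET list in Protocol 7.5.3 includes VascuQol, ABI and the walk test. A patient who leaves after occlusion and attends that visit is in the Month 12 row, probably with a poor value. This stands, and it is why the sizes above are an upper case. It does not close the gap: attendance is requested rather than assured, the ET visit supplies nothing for Months 3, 6 and 9, and it puts an early value under a Month 12 label.

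Second, neither document requires withdrawal when the HAV fails. The SAP's definition of abandonment also covers cases where no action was taken, so patients with an occluded HAV can stay and lower the mean. That is proper in an all-patient summary and is not part of the fault.

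Third, V002 does not show another graft's benefit being credited to the HAV. Protocol 2.4.3 describes five final losses (one replaced, two left occluded after recurrent thrombosis, two who refused intervention) and four withdrawals after occlusion. The replaced patient may be one of those four, and nothing says that this patient gave later values.

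Fourth, results are exploratory, n is printed at each visit, patency rates are reported alongside, and individual values are listed. With 15 patients a diligent reader could join the listings. That limits the harm, but it leaves the reader to construct the summary that the objective asks for.

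**Conclusion.** The concern holds in a limited form. The plan has no rule linking these three measures to HAV status, exit or replacement, so what each visit row describes depends on who attends and what has happened to the limb.

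A reader might infer that the Month 12 result describes only survivors and rescued limbs. The documents do not support that, because of the ET visit and because patients with an occluded HAV may remain. A reader might also infer that V002 proves both routes to bias. It shows that withdrawal after occlusion and replacement occur, not that a replaced patient contributed later data.

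For ABI, the overstatement from exit is at most about 0.05 to 0.06 at 15.8% loss and 0.08 to 0.10 at 25% loss, if the gain is 0.3 to 0.4 with a patent HAV, zero after loss, and no failure supplies a value. ET attendance makes it smaller at Month 12. Upward bias from replacement is likely but not certain. The direction of the error from relabelled ET values is not determined. No size can be given for the walk test or VascuQol. Nothing here affects a hypothesis test, since none is planned. The change is worth making because it is cheap and alters what an uncontrolled study can say about function.

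**What to change.** In SAP 4.4.2, keep the planned table and add the following:

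- **By HAV status.** At each visit, show n and change from baseline for patients whose HAV is patent; occluded or abandoned; or replaced, with other revascularisation of the limb, or amputation. Take patency and date of loss from the data review meeting (SAP 8).
- **ET values apart.** Tabulate ET assessments separately from true Month 12 assessments.
- **One row over all HAV recipients, for each measure.** Give the number and percentage with a patent HAV and improvement at Month 12. Define improvement before the analysis, for example as any increase over baseline. Count HAV loss, amputation, death or exit before Month 12 as not improved.

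The cost is a few table blocks. Patency status is already adjudicated. Amputation and limb revascularisation are named endpoints only after Month 12, so the sponsor should confirm that earlier events can be identified from the adverse event and intervention records. The downsides are small cells (two to four patients without a patent HAV on the figures above), a less favourable summary, and a responder row that partly overlaps with patency. The status split is descriptive: its groups are formed after implantation, and it should not be read as estimating a causal effect.

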4.4.3 Analysis of Long Term Efficacy Parameters

Patient overall survival at 60 months

Patients overall survival (OS) status of alive or death, as well as the date of death and date of last known alive will be collected at the Month 60 visit.

OS is defined as: Date of Death or date of last known alive - Date of Surgery + 1

Patients who are still alive will be censored at the 60 month visit date or last known date alive, whichever occurs last. Median OS will be tabulated and Kaplan Meier (K-M) graph will also be included.

HAV interventions

HAV interventions will be listed.

Evidence of aneurysmal dilatation or stenosis of the HAV

Evidence of aneurysmal dilatation or stenosis of the HAV will be listed.

Patency of the HAV (primary, primary assisted, secondary)

Patency of the HAV (primary, primary assisted, secondary patency rates) will be presented for Months 18, 24, 30, 36, 42, 48, 54 and 60. Clopper-Pearson CIs will be presented for frequency counts of patency rates.

Limb salvage/amputation

Limb salvage/amputation at 18, 24, 30, 36, 42, 48, 54 and 60 months will be listed for all subjects who have not died, withdrawn, or been lost to follow-up.

Surgical Revascularization

Incidence of surgical revascularization of the implanted limb, at the level of the HAV or distal to HAV, will be listed for all patients who have not died, withdrawn, or been lost to follow-up.

VascuQol Quality of Life Questionnaire

VascuQol PAD symptom assessment consists of 25 questions. The total score and the 5 domain scores (Activity, Symptom, Pain, Emotional, and Social) will be recorded in the clinical database at 18, 24, 30, 36, 42, 48, 54 and 60 months. VascuQol results will be listed and summarized for all patients who have not died, withdrawn, or been lost to follow-up.

Final Analysis 17/23

4.4.4 Other Efficacy Variables

High Resolution Ultrasound

Doppler ultrasound (HAV patency) high resolution ultrasound data will be listed.

Time to loss of patency

Time after first implantation of HAV until loss of patency (primary, primary assisted and secondary) will be separately presented in tables using descriptive statistics. The time to loss of patency will be verified during the DRM using all data from the CRF including the information used for patency rates at each visit and information on any AEs and consequent interventions.

Patients discontinued early with the HAV still patent, will be censored at that timepoint.

The median times (or the lower quartile – in case the median is unable to be estimated) will be presented together with the respective 95% CIs using Kaplan-Meier estimates. In case of small numbers of events these analyses may be skipped.

For the 1-year interim analysis, time to loss of patency will be reviewed for the first 12 months, and rates of 3, 6, and 12 months will be presented. For the final analysis, time to loss of patency will be reviewed for the entire study and rates of 3, 6, 12, 24, 36, 48, and 60 months will be presented.

Focused vascular assessment exam will be listed.

Angiography and Endothelium-dependent, flow-mediated vasodilation data will be listed.

5 Safety Analysis

5.1 Vital signs (blood pressure, heart rate, body temperature)

Blood pressure (systolic and diastolic [mmHg]), heart rate (bpm) and body temperature (C) will be presented by descriptive measures for each visit as well as for the absolute change from baseline. Vital signs will be collected up to the Month 12 visit.

5.2 Physical examinations

Physical examinations are collected for each study visit.

- For the 1-year analysis: Results of physical examination will be presented by frequency tabulations for each visit.
- For the final analysis: A shift from baseline to final study visit will be provided.

5.3 **Prior and Concomitant medication**

Medications will be coded by World Health Organization Drug Reference List (WHO-DRL).

Medications will be tabulated by Anatomic Group (Anatomical therapeutic chemical classification [ATC] level 1), ATC level 4, and WHO-DRL preferred term. The number of entries,

Statistical Analysis Plan	Final Analysis
CLN-PRO-004	18/23

as well as the number and percentage of affected patients will be reported.

Previous and concomitant medications will be separately described. A medication can only be categorized as previous or concomitant.

- Previous medications: are defined as those taken within 7 days prior to day 1 and stopped **before** date of first HAV implantation: Stop Date < Day 1
- Concomitant medications are defined as any used within 7 days prior to Day 1 and stopped on or after date of first HAV implantation (≥ Day 1), or which are ongoing from Day 1, or which are taken after date of HAV implantation. If the start or stop date is incomplete and the allocation to previous or concomitant is not clear the medication will be considered to be concomitant.

5.4 Safety Laboratory Parameters

Clinical laboratory variables will be described using summary statistics for the actual values at each visit, as well as for the absolute change from baseline to each visit. The standard error of the mean (SEM) will be included in these tables.

The following laboratory parameters were determined and will be described for the corresponding visits:

Hematology (measured at screening and Month 6)

- Hemoglobin
- Hematocrit
- Red Blood Cells (RBC)
- Absolute Lymphocytes
- Absolute Monocytes
- Absolute Eosinophil
- Absolute Basophil
- White Blood Cells (WBC)
- Absolute Neutrophil Count

Clinical Blood Chemistry (measured at screening and Month 6)

- Sodium
- Potassium
- Calcium

Final Analysis 19/23

- Blood Urea Nitrogen (BUN)
- Total Bilirubin
- Creatinine
- Glucose (non-fasting)
- Albumin

Coagulation (measured at screening and Month 6)

- International Normalized Ratio (INR)
- Activated Partial Thromboplastin Time (aPTT)

Immunology (measured at screening and Month 6)

• PRA sample collection date will be listed.

Hematology, chemistry and coagulation values are quantitative. The findings (normal, abnormal clinically significant [CS], abnormal not clinically significant [NCS]) are available for each test and will be provided in the listings.

The laboratory values were provided by local laboratories and unit values are not consistent across sites. The values used for the table summary will be **conventional units** and will be calculated by a conversion method.

6 Adverse Events (AEs)

Adverse events that started before HAV implantation are collected and documented in the EDC as medical history.

Adverse events will be coded by MedDRA. Presentation of adverse events will be the number of entries, as well as the number and percentage of affected patients. Tabulations will show numbers of adverse events by system organ class (SOC), preferred term (PT), and severity.

Each documented adverse event per patient will be considered, i.e. if a patient experienced the same adverse event (identical adverse event description) more than once during study duration, all events will be counted.

To give an overview of all adverse events a frequency table will be prepared showing the following information (displaying number of patients, percentage of patients and number of events).

Overview table:

- any AEs
- any serious AEs (SAEs)

Final Analysis 20/23

any AEs leading to death as outcome

Additionally, the following tables (grouped by MedDRA terms [SOC and PT]) will be presented:

- AEs
- SAEs
- AEs by severity
- Deaths
- Leading to premature discontinuation

HAV Complications

AE relationship is recorded on the AE eCRF. For purpose of the DMC summary, any AE that is related to the HAV will be considered as a HAV complication.

The incidence of HAV complications (aneurysm formation, pseudoaneurysm formation, anastomotic bleeding or spontaneous rupture, HAV removal, HAV infection and significant local inflammation at the HAV implantation site will be identified during DRM and will be separately tabulated. HAV complications will also be listed in terms of incidence, severity, and (where appropriate) time to onset and duration.

7 Analysis of Other Variables

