### 7.3. Laboratory Evaluations

#### 7.3.1. Clinical and Research Laboratory Evaluations and Specimen Collection

The following parameters will be measured at screening and Month 6:

- Hematology: hemoglobin, hematocrit, red blood cells (RBC), WBC with differential, platelet count
- Clinical chemistry: sodium, potassium, calcium, blood urea nitrogen (BUN), creatinine, albumin, total bilirubin, glucose (non-fasting)
- Urine or serum human chorionic gonadotropin (HCG) pregnancy test for WOCBP defined as not sterile or not > 1 year postmenopausal (screening only)
- Coagulation: INR and activated partial thromboplastin time (aPTT)

- HbA1c (Screening only)
- PRA

All laboratory tests (except assay of PRA) will be conducted at certified hospital laboratories. Routine monitoring, maintenance or calibration of laboratory equipment is required per local site procedures. Samples for analysis of PRA will be shipped to Humacyte for analysis at a central laboratory.

Details concerning sample collection and processing can be found in the Study Manual.

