# 9.2. Safety Analyses

Safety analyses will be performed on all patients who have an HAV implanted when the final patient enrolled reaches 12 months post-implant

Incidence of HAV aneurysm formation (true or pseudo), anastomotic bleeding or spontaneous rupture, HAV infection, HAV removal, and significant local inflammation at the HAV implantation site will be separately tabulated and listed.

Adverse events will be coded using Medical Dictionary for Regulatory Activities (MedDRA) terms. Adverse events will be listed and summarized by system organ class, preferred term, incidence, severity, and duration. HAV complications will be listed in terms of incidence, severity, and (where appropriate) time to onset and duration. Serious adverse events will be summarized separately. Any premature discontinuations due to adverse events and deaths will be listed and summarized.

Laboratory data, including PRA, will be listed and summarized using appropriate descriptive statistics at each visit and for the absolute change from baseline values for all post-surgery visits. The closest non-missing values prior to surgery on Day 1 will be used as baseline values.

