2.2 Secondary Safety Endpoints

- Change from baseline in PRA
- Change from baseline in hematology, coagulation, and clinical chemistry parameters

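### The SAP's hematology list leaves out platelet count, which the protocol measures at screening and Month 6 and commits to summarising

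*SAP*

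**What the plan says.** Protocol 7.3.1 sets the timing with "The following parameters will be measured at screening and Month 6" and defines the panel as "Hematology: hemoglobin, hematocrit, red blood cells (RBC), WBC with differential, platelet count". Protocol 9.2 says that laboratory data "will be listed and summarized using appropriate descriptive statistics at each visit and for the absolute change from baseline values" for post-surgery visits, with no analyte excepted.

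The secondary safety endpoint in SAP 2.2, worded the same way in protocol 4.2.2, is "Change from baseline in hematology, coagulation, and clinical chemistry parameters".

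SAP 5.4 opens with a general rule: "Clinical laboratory variables will be described using summary statistics for the actual values at each visit", together with the absolute change from baseline. It then narrows to a list introduced by "The following laboratory parameters were determined and will be described for the corresponding visits". The hematology part of that list has nine entries: hemoglobin, hematocrit, RBC, absolute lymphocytes, monocytes, eosinophils and basophils, WBC, and absolute neutrophils. Platelet count is not there, and we found it nowhere else in the SAP text available.

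**The concern.** The SAP list has no wording that leaves it open to further analytes, so a programmer building the laboratory tables would take it as the specification. The hematology endpoint would then be reported without one of the parameters that the protocol measures for it, and the SAP would not carry out protocol 9.2 in full.

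Platelet count is not a peripheral item in this trial. Protocol 5.1.1 sets a platelet threshold for entry (at least 100,000/mm³), protocol 2.5.1 names conduit thrombosis, bleeding and hematoma among the risks, and protocol 6.8.1 expects long-term antiplatelet therapy. A reader of the study report would expect platelets beside the other hematology values, and the SAP as written summarises basophils and eosinophils but not platelets.

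**Working it through.** No power, alpha or event figure is involved. The check is an item-by-item comparison of protocol 7.3.1 with SAP 5.4 for the three panels measured at both screening and Month 6. HbA1c and the pregnancy test are left out because they are done at screening only. PRA is left out because SAP 5.4 handles it separately. One counting assumption is needed: the protocol does not name the cells of the WBC differential, so WBC with differential is counted as WBC plus the five cell types that the SAP names.

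| Panel | Protocol 7.3.1 | SAP 5.4 | Missing from SAP |
|---|---|---|---|
| Hematology | 10 (hemoglobin, hematocrit, RBC, WBC, 5 differential items, platelets) | 9 | Platelet count |
| Clinical chemistry | 8 (sodium, potassium, calcium, BUN, creatinine, albumin, total bilirubin, glucose) | 8 | None |
| Coagulation | 2 (INR, aPTT) | 2 | None |
| Total | 10 + 8 + 2 = 20 | 9 + 8 + 2 = 19 | 20 − 19 = 1 |

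**What is lost.** For each listed analyte the SAP gives three sets of statistics: screening values, Month 6 values, and the change between them. For platelets it gives none of the three. SAP 1.5 reports 15 patients recruited, so at most 15 patients would contribute a change value.

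**Is it an artefact of the text?** This looks unlikely. The hematology bullets in SAP 5.4 run without a break; the page break falls later, within the chemistry list after calcium. The list in the superseded SAP version 1.0 also lacks platelets. Between the two versions RBC was added, and HbA1c, AST, ALT, alkaline phosphatase and GGT were dropped. Those edits bring the current list into line with protocol 7.3.1 in every respect but platelets. That pattern suggests an oversight that survived a revision, though it does not prove one.

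**The case against.** Several points on the other side have weight.

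- **The general rule may cover it.** The opening sentence of SAP 5.4 and protocol 9.2 can both be read as including every laboratory variable. The explicit list is nevertheless what defines the tables. If platelets were meant to be included, adding the row only records that intent.
- **A reader might infer that a platelet change would be invisible to the DMC and to readers of the report.** The documents do not support that. Protocol 8.1 counts an abnormal laboratory finding as a possible adverse event, and protocol 8.5.2 grades abnormal laboratory values, so an abnormality reported that way would reach the adverse event tables. SAP 3.4 has the 1-year listings show all available study data. DMC reports are mentioned in SAP 3.4 without being specified by analyte, and the DMC works under a separate charter (protocol 8.7).
- **A reader might take the 35% graft thrombosis rate in the earlier PAD study (protocol 2.4.3) as a measure of this gap.** It is not one. No document links a Month 6 platelet count to thrombosis, and a single sample months after surgery says little about intraoperative heparin.
- **The values may not be in the database.** The SAP says the listed parameters were determined, and platelets are not listed. SAP version 1.0 was written against the annotated eCRF and also lacks them. Eligibility requires a screening value, but nothing confirms that Month 6 values were captured.
- **The exclusion may have been declared.** The SAP contents show a section 10 on changes from the protocol. For the current version that section is not in the text available to us, so a stated reason cannot be ruled out.

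These points limit the consequence and leave the cause open. They do not remove the mismatch between the two lists.

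**Conclusion.** The point holds. SAP 5.4 omits one analyte that protocol 7.3.1 measures and protocol 9.2 commits to summarising, so the hematology secondary safety endpoint is incompletely implemented. This is an incorrect list rather than a missing level of detail.

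Its size is modest. It affects a descriptive summary with one scheduled post-baseline value, in a study without hypothesis testing whose results the SAP treats as exploratory. No primary endpoint, estimate or design figure changes.

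The conclusion assumes that the enumerated list governs the tables and that no exclusion is declared in the part of the SAP we could not see. It does not extend to a claim that platelet abnormalities would go undetected.

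**What to change.** Add platelet count to the hematology list in SAP 5.4, with actual values at screening and Month 6 and the absolute change from baseline, as for the other parameters. The list then has 10 hematology items and matches protocol 7.3.1. No separate listing rule is needed, because SAP 5.4 already sends the normal or abnormal finding for each test to the listings.

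First confirm that Month 6 platelet values are in the database. If they are, the cost is one line in the SAP and one more parameter in an existing table. If they were not captured, or if platelets were left out on purpose, state this in the SAP as a departure from the protocol, with the reason.
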